5.1 Screening Phase

Subjects who are HIV positive, have been on HAART for ≥ 6 months and are virally suppressed will be screened for participation in the study using the inclusion and exclusion criteria listed below. Eligible patients will be approached to consent to the study. Those who agree to participate will be screened with an echo to determine if they are EF eligible and classified as DD+ or DD-. Diastolic dysfunction criteria are:

- (1) LVEF $> 50\%$
- (2) Evidence of impaired LV relaxation (septal $e' < 7\text{cm/s}$ or lateral $e' < 10\text{cm/s}$)
- (3) Evidence of chronically elevated LV filling pressure or LVH (or concentric remodeling)
 - (a) LA volume index $> 28\text{ml/m}^2$ or

- (b) LV hypertrophy (LV mass index $>95\text{g/m}^2$ in women, $>115\text{g/m}^2$ in men or
- (c) Concentric LV remodeling (relative to wall thickness >0.42)

[figure not shown]
5.2 Baseline Evaluation Phase

Subjects who qualify for the study will have a detailed medical history, physical exam, blood drawn, and cMRI tests acquired.

5.3 Follow-up Phase

There is no follow-up phase in this study. Study participation will conclude after the Baseline Visit.

6 STUDY FLOW DIAGRAM

7 STUDY POPULATION AND ELIGIBILITY CRITERIA

Study Population

Subjects who are receiving care at a site participating in the Heart Failure Clinical Research Network program, are HIV positive, have been on HAART for ≥ 6 months and are virally suppressed will be screened for participation in the study using the inclusion and exclusion criteria listed below.

Enrolled subjects will be compared to non-HIV subjects with DD (HIV-/DD+) from MESA.

MESA Longitudinal Cohort Study

MESA is an NIH-funded longitudinal cohort study that recruited 6,814 participants from 6 centers (Winston-Salem, Los Angeles, Baltimore, Chicago, New York, Minneapolis/St Paul). At enrollment during 2000-2002, all participants were aged 45-84 and free of CV disease (CVD). There has been continuous surveillance for CVD events including HF. MESA Exam 6 will enroll

3500+ participants and will be conducted from September 2016 to March 2018. MESA Exam 6 will include comprehensive echocardiography, arterial stiffness measures, and blood collection for biomarkers. There is a concurrent echocardiographic study in MESA exam 6 that has been funded (R01 HL127028, PI [name]) that will recruit 3500+ participants from 2016-17 and will form the cohort for HIV-/DD+ for the present study; the HIV study and MESA will have an identical dynamic echocardiography protocol, with a single reading center at Northwestern University for both studies.

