3 INTRODUCTION

3.1 Background and Significance

Heart failure (HF) patients have $\approx 50\%$ mortality risk within 5 year of diagnosis, underscoring the need to better understand determinants of HF risk in order to develop effective screening and prevention interventions. An emerging risk factor for HF is human immunodeficiency virus (HIV) infection. HIV-related HF was identified as a major priority by the 2015 NHLBI AIDS Working Group. Since the early reports from the 1980s, the pattern of left ventricular (LV) dysfunction in HIV has evolved. Studies in the modern anti-retroviral therapy (ART) era have demonstrated lower rates of LV systolic dysfunction¹ but strikingly higher rates of diastolic dysfunction (DD), ranging from 26-50% as compared to 6-30% in the general population.² The mean age of HIV+ subjects with DD ranged from 38-49 years,¹ which is at least a decade younger than DD onset in the general population.³ DD is associated with atrial fibrillation, HF, and mortality.⁴⁻⁶ Thus there is a concern that the next epidemic in HIV+ patients will be HF with preserved ejection fraction (HFpEF). There is an unmet need to study DD in HIV+ patients to understand why they develop more prevalent and early onset DD.

Diastolic Dysfunction and Heart Failure

Left ventricular (LV) diastolic dysfunction (DD) is frequently present in older adults, with a prevalence ranging from 6-30% depending on the methodology, definition, and population studied. DD is associated with the development of atrial fibrillation and heart failure (HF), and portends higher risk for all-cause mortality. Previous studies have shown that DD is associated with obesity, hypertension, and metabolic syndrome, conditions that are associated with elevated inflammatory cytokines and endothelial dysfunction. It is important to note that DD is not the same as diastolic heart failure or HF with preserved ejection fraction (HFpEF). DD (also known as subclinical DD or preclinical DD) is an asymptomatic pathophysiological abnormality that precedes overt, symptomatic HF. As such, it is a clear representation of ACC/AHA Stage B HF (asymptomatic cardiac structural and functional abnormalities). It is critically important to understand DD prevalence, pathogenesis, and sequelae given its association with significant morbidity and mortality.

HIV-Related Diastolic Dysfunction and Heart Failure

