6. LVEF $> 50\%$

7.2 Exclusion Criteria

1. Past EF $< 50\%$
2. Moderate or severe valve stenosis or regurgitation, or past repair or replacement
3. Percutaneous or surgical revascularization or active angina
4. Persistent atrial fibrillation
5. BP > 160 mmHg SBP or > 100 mmHg DBP
6. Comorbid inflammatory disease (e.g. RA or SLE)
7. Active cancer or cancer chemotherapy treatment in the prior year (except skin cancer that did not require chemotherapy or radiation)
8. Chronic use of steroids or anti-inflammatory therapy
9. GFR < 30 mL/min
10. Active in a clinical trial with investigational product
11. Pregnant or lactating females
12. Contraindication to cMR or gadolinium injection (such as severe claustrophobia, metal implants, etc.)

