13.2 Power Calculations and Statistical Analysis for Biomarkers

The primary statistical comparison for Aim 1a is the between group (the HIV+/DD+ and HIV+/DD- cohorts) difference in log-transformed IL-6 biomarker levels. Log-transformed IL-6 (log pg/ml) is expected to have a standard deviation of approximately 0.75.⁵² Sample sizes of 100 subjects in each group will provide 80% and 90% power to detect differences of 0.30 and 0.35 (log pg/ml), respectively. These sample size calculations were based on a two-sample t-test with a two-sided type I error of 0.05. Additionally these calculations suggest that any comparison of (properly transformed) continuous variables between the HIV+/DD- and HIV+/DD+ cohorts will have 80% and 90% power to detect differences of 0.40 and 0.46 standard deviations, respectively. Comparisons between the HIV+/DD+ or HIV+/DD- cohorts and the HIV-/DD+ cohort will have greater power due to the larger number of subjects in the HIV-/DD+ cohort. Statistical summaries will use median (25th, 75th percentiles) and mean (standard deviation) for continuous measures and frequencies (percentages) for categorical variables. Because many biomarkers are expected to be right-skewed, we will log-transform each marker or use another appropriate transformation to normalize its distribution. Unadjusted comparisons between groups will be based on t-tests after the appropriate transformations for continuous measures and chi-square tests for categorical measures. For Aim 1a, propensity scores will be the primary tool used to obtain balanced comparisons between cohorts. The propensity score is defined as the probability of having group membership (e.g. HIV+/DD+) conditional on observed covariates and is a commonly used balancing score used in observational studies.⁵³ Three different methods of propensity score adjustment will be applied. The primary analysis method will be based on inverse probability weightings. Secondary approaches will be based on full propensity score matching and doubly-robust estimation.^{54, 55} Distributional overlap and covariate balance will be assessed using the recently developed best practices for propensity score analyses.⁵⁶ The primary adjusted analysis of IL-6 levels between cohorts will be conducted at the two-sided 0.05 level.

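### The Section 7.2 exclusions are stated only for the HIV+ cohort, so the contrasts with MESA HIV-/DD+ subjects can carry selection bias of unknown size and direction

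*Combined protocol and SAP*

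**What the plan says.** Section 7 opens by naming who is screened with the inclusion and exclusion lists: patients at network sites who are HIV positive, have had at least 6 months of HAART and are virally suppressed. The comparator follows in a separate sentence: "Enrolled subjects will be compared to non-HIV subjects with DD (HIV-/DD+) from MESA".

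The MESA description in Section 7 gives an entry age of 45-84, absence of cardiovascular disease at entry in 2000-2002, and an Exam 6 running from September 2016 to March 2018. It adds that "There has been continuous surveillance for CVD events including HF". The Exam 6 echo study, with 3500 or more participants, supplies the HIV-/DD+ group. What the section harmonises between the two studies is the echo protocol and the reading center. Eligibility is not mentioned.

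Section 7.2 excludes, among others, past EF below 50%, significant valve disease, revascularization or active angina, persistent AF, high blood pressure, inflammatory disease such as RA or SLE, active cancer or recent chemotherapy, GFR below 30, and "Chronic use of steroids or anti-inflammatory therapy".

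Section 4 sets HIV+/DD+ against HIV-/DD+ on IL-6 and hsCRP (Aim 1c), phenogroups (1d), fibrosis, arterial inflammation, oxidative stress and coagulation markers (2b), left atrial strain (3a), and troponin and NT-proBNP (3b).

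**The concern.** The hypotheses in Aims 1c, 2b, 3a and 3b are about the effect of HIV among people with DD. If one group has been cleared of conditions that move the outcome and the other has not, part of any difference reflects that clearing and not HIV. The overlap between exclusions and outcomes is direct. Inflammatory disease, cancer and steroid or anti-inflammatory use bear on IL-6 and hsCRP. Revascularization, AF, valve disease and low GFR bear on troponin, NT-proBNP and left atrial strain.

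Freedom from cardiovascular disease at MESA entry gives little protection. It is old by Exam 6, and it never covered inflammatory disease, cancer, renal function or drug use. A large comparator group does not help either: it shrinks the standard error around a biased difference.

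**Working it through.** **1. The plan's own figures.** Section 13.2 states the calculation is "based on a two-sample t-test with a two-sided type I error of 0.05"; log IL-6 "is expected to have a standard deviation of approximately 0.75". The claim is: "Sample sizes of 100 subjects in each group will provide 80% and 90% power to detect differences of 0.30 and 0.35 (log pg/ml), respectively". With d = difference/SD and SE = sqrt(2/100) = 0.1414 in SD units, power = Φ(d/SE − 1.960).

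- 0.30/0.75 = 0.40 SD: 0.40/0.1414 = 2.828, power 80.7% (80.4% by noncentral t).
- 0.35/0.75 = 0.467 SD: power 91.0% (90.7%).
- 0.46 SD: power 90.2% (89.9%).

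The stated power reproduces. No figure in the plan is disputed. These figures concern the two HIV+ groups. For MESA the plan claims higher power but gives no number of subjects.

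**2. Which selection applies to whom.**

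| | HIV+ cohort | MESA HIV-/DD+ |
|---|---|---|
| DD and LVEF >50% | Section 5.1, 7.1 | Section 5.1 definition, taken to carry over |
| Cardiovascular history | Section 7.2, current | At entry, 2000-2002 |
| Inflammatory disease, steroids/anti-inflammatories, cancer, GFR, BP | Section 7.2 | Nothing stated |

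By calendar year the gap from MESA entry to Exam 6 is 2016 − 2002 = 14 to 2018 − 2000 = 18 years.

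**3. Is there an analytic safeguard?** Propensity methods are specified for Aim 1a (13.2), Aim 2a (13.4) and the echo comparison (13.7). The stated primary comparisons there are within the HIV+ cohorts, reading the repeated group label in 13.7 as a slip. The regression in 13.5 also compares HIV+/DD+ with HIV+/DD-. For the MESA biomarker contrasts no propensity method or covariate list is given.

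**4. Illustration of size.** Assumptions, not document figures: a share f of MESA DD+ subjects has an excluded condition, and each is shifted on average by d SD. Bias = f × d. The MESA DD+ count M is also assumed: 6-30% (the general DD prevalence in Section 3.1) of 3500 gives 210 to 1050. SE = sqrt(1/100 + 1/M) = 0.1215 for M = 210 and 0.1047 for M = 1050. With no true HIV effect, two-sided rejection = Φ(−1.960 + bias/SE) + Φ(−1.960 − bias/SE).

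| f | d (SD) | Bias (SD) | Bias (log IL-6, × 0.75) | Rejection, M = 210 to 1050 |
|---|---|---|---|---|
| 10% | 0.25 | 0.025 | 0.019 | 5.5-5.7% |
| 20% | 0.5 | 0.10 | 0.075 | 13-16% |
| 40% | 1.0 | 0.40 | 0.30 | 91-97% |

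For the middle row: 0.10/0.1215 = 0.823, giving 0.128 + 0.003 = 13%; 0.10/0.1047 = 0.956, giving 0.158 + 0.002 = 16%. If that shift raises the marker in MESA, power for a true 0.40 SD excess in HIV+ falls from 91-97% to 70-82%: Φ(0.30/SE − 1.960). If it lowers the marker, the apparent excess is inflated instead. The formula ignores the small extra spread from mixing affected and unaffected subjects (0.2 × 0.8 × 0.5² = 0.04 against a variance of 1).

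**5. Cost of restricting MESA.** Removing 10-50% (assumed) leaves 189-105 of 210, or 945-525 of 1050. Power at 0.40 SD becomes 89.9-81.7%, or 96.7-95.6%.

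**The case against.** The plan does not say that Section 7.2 will be waived for MESA. Section 13.1 promises an analysis plan before the data are analyzed. Inclusion item 4 is marked as applying to the HIV-positive cohort only, which suggests the list may have been meant for more than one cohort. The content of the Section 6 flow diagram was not available to this check. All of that stands, so this is an omission and not a declared choice. But inclusion items 3 and 5 carry no such mark and cannot be met by HIV-negative subjects, so the list as written does not govern MESA.

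The comparator is also not wholly unselected: DD itself requires LVEF above 50%, and MESA entry required absence of cardiovascular disease. That stands too, within the limits of its age and scope.

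A reader might infer that propensity weighting could never repair the problem. That goes too far. If the excluded condition is in the model and the target is the HIV+ population, comparator weights are e/(1 − e), where e is the probability of being HIV+. A MESA subject with an excluded condition has e = 0 and gets zero weight. Weighting to the combined population does fail, because no HIV+ subject can stand in for those MESA subjects. The plan names neither target nor covariates for these contrasts.

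A reader might also take Section 3.1, where "DD (also known as subclinical DD or preclinical DD) is an asymptomatic pathophysiological abnormality that precedes overt, symptomatic HF", to mean that clinical heart failure should be excluded from both cohorts. That is a separate and weaker question about eligibility on both sides. Recruitment runs through HIV clinics, and past EF below 50% is already excluded.

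**Conclusion.** The concern holds as a gap in the stated design: followed as written, the plan compares a group screened under Section 7.2 with one that is largely unscreened on the same conditions. Aims 1c, 2b, 3a and 3b are exposed in their HIV+/DD+ versus HIV-/DD+ contrasts, and the phenogroup comparison in Aim 1d is affected. Aims 1a, 1b and 2a, which stay within the HIV+ cohorts, are not.

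The size is not known. The 0.10 SD bias and the 13-16% false rejection rest on an assumed 20% share, an assumed 0.5 SD shift and an assumed 210-1050 MESA DD+ subjects; the wider table shows how much the answer depends on them. A reader might infer that the bias mostly hides the expected HIV excess, or that it rivals the difference the study is sized for. The documents support neither. They give no Exam 6 prevalence of the excluded conditions. Steroid or anti-inflammatory users left in MESA could push the other way. The 0.30 log pg/ml planning difference belongs to Aim 1a, which this point does not touch.

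**What to change.** State in Section 7 that the HIV-/DD+ comparators are MESA Exam 6 participants who meet the Section 5.1 DD criteria and have none of the Section 7.2 exclusions that can be ascertained from MESA data. The cMR/gadolinium item need not apply. Apply the restriction before analysis, list the exclusions that cannot be ascertained, and report how many comparators remain. Restriction removes the non-overlap on those conditions directly, whichever weighting target is later chosen. If weighting is also intended for these contrasts, name its target population and covariates.

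The cost is a filter on comparator data and a short addition to Section 7, plus a smaller MESA group. The higher power that Section 13.2 claims for MESA contrasts holds while more than 100 comparators remain; on the assumed counts, even halving 210 leaves 105. Ascertainment will be incomplete. Section 13.3 lists clinical, medication, laboratory and imaging data from MESA visits, but the documents do not say whether past EF, RA or SLE, or recent chemotherapy are recorded. Bias from any item that cannot be ascertained would remain and should be acknowledged when the results are reported.

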7.1 Inclusion Criteria

1. Age ≥ 40 years
2. Willingness and ability to provide informed consent
3. HIV antibody positive
4. On HAART for ≥ 6 months (HIV positive cohort only)
5. History of adequate viral suppression as defined by most recent HIV RNA level < 200 copies/mL performed in the past 6 months
6. LVEF $> 50\%$

7.2 Exclusion Criteria

1. Past EF $< 50\%$
2. Moderate or severe valve stenosis or regurgitation, or past repair or replacement
3. Percutaneous or surgical revascularization or active angina
4. Persistent atrial fibrillation
5. BP > 160 mmHg SBP or > 100 mmHg DBP
6. Comorbid inflammatory disease (e.g. RA or SLE)
7. Active cancer or cancer chemotherapy treatment in the prior year (except skin cancer that did not require chemotherapy or radiation)
8. Chronic use of steroids or anti-inflammatory therapy
9. GFR < 30 mL/min
10. Active in a clinical trial with investigational product
11. Pregnant or lactating females
12. Contraindication to cMR or gadolinium injection (such as severe claustrophobia, metal implants, etc.)

7.2.1 Exclusion Criteria for T1 mapping substudy

1. Atrial Fibrillation at time of MRI

8 SCREENING PROCEDURES

8.1 Pre-screening

Patients meeting eligibility criteria will be approached regarding participation in the study.

8.2 Screening Phase

Subjects who sign the informed consent document will have an echocardiogram (echo). If the subject continues to meet the inclusion criteria, they will proceed to the baseline

procedures. Women of child bearing potential who are not post-menopausal will receive a pregnancy test (urine or serum) within 48 hours prior to the MRI.

9 BASELINE EVALUATION

9.1 Baseline Evaluation Phase

Detailed data will be collected to clinically characterize patients including:

- Demographics
- Risk factors and duration of HIV
- Illicit drug and tobacco use
- Alcohol use
- Co-infections including hepatitis B and C
- Comorbidities including diabetes mellitus, hypertension, chronic kidney disease, body mass index and dyslipidemia
- Medications, including previous antiretroviral therapy
- Physical examination
- Medical history
- Collection of historical bloodwork (chemistry and hematology) values and HIV specific laboratory testing including CD4 count and HIV RNA levels (no blood will be drawn for this purpose)
- Past cardiac procedures
- Past imaging study results
- Kansas City Cardiomyopathy Questionnaire (KCCQ)
- EKG
- Blood draw for biomarkers, -omics, and biorepository (if consented to biorepository)
- cMRI
- cMRI T-1 mapping substudy, if available at the center and subject consented to additional testing, including a hematocrit lab draw to calculate extracellular volume

10 FOLLOW-UP EVALUATIONS

There are no follow-up visits nor follow-up procedures in this protocol.

11 OUTCOME DETERMINATIONS

Understanding DD pathogenesis in HIV will allow for the identification of treatment paradigms for these patients at risk of HF, which can be very challenging to treat once HF is clinically overt.

11.1 Biomarkers

The biomarkers selected for the various pathophysiologic domains represent biomarkers that have either an established evidence base in HIV, or domains applicable to the hypothesized cardiovascular pathophysiology in HIV DD. We propose to study biomarkers related to

inflammation, immune activation, fibrosis and remodeling, coagulation, and oxidative stress.

TABLE 1

Biomarkers			
Inflammation	IL-6, hsCRP	Arterial inflammation	Oxidized LDL, LpPLA2
Immune activation	sCD163, sCD14, monocytes expression of CD14 and CD16, T cell activation and subsets: Th1, Threg, CD4+, CD8+ T cell activation	Fibrosis and remodeling	ST2, GDF-15, C1P:MMP-1 ratio, Gal 3
Coagulation	D-dimer, fibrinogen	Oxidative stress	Myeloperoxidase
Necrosis	hs troponin I	Stress	NTproBNP

In HIV infection, biomarkers of immunity and inflammation are elevated even in the setting of treated suppressed HIV compared to non-infected controls, and higher levels are associated with adverse events and mortality.¹²⁻¹⁸ **IL-6** is associated with an increased risk of CVD events and mortality in HIV+ subjects. Highest quartile of IL-6 is associated with 8-fold increased risk of mortality in HIV. IL-6 and **CRP** have been shown to be associated with 4 and 2-fold increased risk of CVD events, respectively. Higher levels of inflammation markers in HIV+ subjects are associated with higher viral load. IL-6 and **D-dimer** levels may mediate the relationship between HAART interruption and risk for mortality. T cell activation has been associated with carotid IMT and arterial stiffness in HIV-infected individuals.¹⁹⁻²¹ Monocytes are classified on the basis of their **CD14 and CD16** surface expression into *classic* (CD14++/CD16-), *intermediate* (CD14++/CD16+) and *non-classic* (CD14low/+CD16++) subsets.²² In HIV, expansion of intermediate and non-classical monocytes has been shown, however only the expansion of non-classical monocyte persists after starting HAART.²³ Intermediate monocytes²⁴ and CD16+ monocytes expressing CX3CR1²⁵ have been associated with subclinical atherosclerosis. Which features of peripheral monocytes are related to the increased DD and HF risk in treated HIV is not known. Circulating soluble CD163 (**sCD163**) is a scavenger receptor found on monocytes and shed by proteolytic cleavage after pro-inflammatory stimulation.^{26, 27} HAART can reduce cCD163 in HIV.²⁸ Elevated levels of sCD163 are associated with coronary plaque¹⁶ and shortened telomere length²⁹ in HIV.

Soluble ST2 (**sST2**), predominantly released by endothelial cells,^{30,31} along with being a marker of inflammation, promotes cardiac fibrosis by acting as a decoy receptor for IL-33, preventing IL-33 binding with its ligand, the myocyte bound ST2 receptor. Elevated concentrations of sST2 are associated with mortality and DD in the general and in those with HIV.^{32,33} **Oxidized LDL** is associated with non-calcified plaque in HIV.³⁴ **Galectin-3** is released by activated macrophages and has been shown in animal models to be associated with cardiac fibrosis.³⁵ Galectin-3 levels may be upregulated in HIV.³⁶ Galectin-3 is associated with cardiovascular events and death.³⁷ Galectin-3 is associated with carotid intima-media thickening in women with HIV.³⁸ **GDF-15**, a biomarker produced by both myocytes and endothelial cells, is an independent prognostic marker of death in HIV and adverse CV outcomes in multiple non-HIV cohorts.^{32,33,39}

Biomarkers representing myocardial injury (**hs-cTnI**) and strain (**NT-proBNP**) inform the role of inflammation on preclinical myocardial disease. hs-cTnT is a powerful prognosticator of CVD events, including HF.⁴⁰⁻⁴² Studies have shown a strong association of hs-cTnT levels with LV mass and function in general.^{40,43} NT-proBNP levels also predict the risk of incident HF.^{44,45} NT-

proBNP may predict CVD events in HIV.⁴⁶ NT-proBNP levels are inversely associated with decreased radial strain, a subtle measure of systolic dysfunction.⁴⁷ In HIV NT-proBNP remains a cardiac specific marker of strain that is likely preceded by preclinical evidence of myocardial injury and potentially fibrosis.

